9.1.2. Serious Adverse Event (SAE)

A serious adverse event is an AE that is fatal or life threatening, requires inpatient hospitalization or prolongation of existing hospitalization (for > 24 hours), persistent or significant incapacity or substantial disruption of the ability to conduct normal life functions, or is a congenital anomaly/ birth defect, or results in any important medical event that may not result in death, be life threatening, or require hospitalization may be considered an SAE when, based upon appropriate medical judgment, may jeopardize the subject and may require medical or surgical intervention to prevent any of the above outcomes. A “life-threatening” adverse event places the patient at immediate risk of death in the judgment of the investigator or sponsor.

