9.1.3. Severity Rating

The investigator will evaluate the severity of each adverse event. NCI Common Terminology Criteria for Adverse Events (CTCAE v.4.0) or study specific toxicity tables provided in the protocol define severity. If not included in CTCAE v.4.0, severity is expressed in numerical grade using the following definitions:

- Grade 1: Mild-asymptomatic or mild symptoms; clinical or diagnostic observations only; intervention not indicated.
- Grade 2: Moderate-minimal, local or noninvasive intervention indicated; limiting age appropriate instrumental ADL.
- Grade 3: Severe-severe or medically significant but not immediately life-threatening; hospitalization or prolongation of hospitalization indicated; disabling; limiting self-care ADL.
- Grade 4: Life-threatening consequences; urgent intervention indicated.
- Grade 5: Death related to AE

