10.0 Recording and Reporting Responsibilities

10.1. Site Recording responsibilities:

Upon identification of an AE or SAE, the site investigator will utilize the above definitions to properly classify the event. Each category listed above must be recorded for each event. All AEs and SAEs will be recorded in the "AE case report forms" (CRF) and in progress reports with details about the grade and attribution of each episode, action taken with respect to the study drug, and the patient's outcome will be recorded in the CRF. All events will be recorded on case report forms for the duration of the study until they resolve.

All SAEs will be recorded on the FDA MedWatch form 3500a. The principal investigator has the obligation to report all serious adverse events to the FDA (if applicable), IRB, and Novartis Pharmaceuticals Drug Safety and Epidemiology Department (DS&E).

10.2. Site Reporting responsibilities:

- 1) The investigator/ site is responsible to report all SAEs that occur on or after the first day of study treatment to the sponsor within 24 hours of becoming aware of the event. All subsequent SAEs must be reported for up to 30 days after the last treatment.

Each investigator is responsible to report all AEs/SAEs to their local IRB following guidelines set by that IRB. The FCCC OCR reserves the right to request an event be

reported to the IRB at their discretion. Copies of events reviewed by the IRB must be sent by email to [contact].

- 2) If the investigator or IRB feels the event warrants a revision to the informed consent that was not already initiated by the OCR, draft revisions will be made in track changes and submitted to the OCR for consideration. Any consent revisions must receive OCR approval prior to submission to the IRB.
- 3) Any investigator who is in doubt of whether a particular AE needs to be reported is directed to call the Study Monitor for confirmation with the Sponsor-Investigator.
- 4) If the results of an investigator or OCR investigation show an adverse event not initially determined to be reportable is so reportable, the investigator will report the event following the above guidelines based on the date the determination is made.
- 5) Copies of all related correspondence and reporting documents must be submitted to the ISRU and will be maintained in the trial master file.

The participating site should report events to:

Investigator-Sponsored Research Unit
Office of Clinical Research
Fox Chase Cancer Center
[contact]

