10.3. Sponsor Reporting Responsibilities:

- 1) Adverse events which meet all of the following criteria must be reported to all participating institutions for IRB submission within 2 weeks of notification of the event.
 - Unexpected (in terms of nature, severity, or frequency) given (a) the research procedures that are described in the protocol-related documents, such as the IRB-approved research protocol and informed consent document; and (b) the characteristics of the subject population being studied;
 - Possibly related to participation in the research (possibly related means there is a reasonable possibility that the incident, experience, or outcome may have been caused by the procedures involved in the research); and
 - Serious (refer to above definition) or otherwise one that suggests that the research places subjects or others at a greater risk of physical or psychological harm than was previously known or recognized.
- 2) If the adverse event requires modification of the study protocol and informed consent, these changes will be provided to all participating institutions in the form of an amendment from the ISRU for each site's IRB of record along with the report of the adverse event.
- 3) Copies of all related correspondence and reporting documents will be maintained in a centralized regulatory file for this study within the OCR.

- 4) SAEs that are related, unexpected, fatal, or life-threatening are reportable through the Food and Drug Administration (FDA) MedWatch program by telephone or fax no later than 7 calendar days after initial receipt of the information. Further information on the timing of submissions is as directed by FDA guidelines (www.fda.gov/medwatch/index.html). Serious, unexpected events that suggest significant clinical risk will be submitted to within 15 calendar days after initial receipt of this information.

Food and Drug Administration:
[contact]
[contact]
<http://www.fda.gov/medwatch/report.htm>

- 5) The investigator must assess and record the relationship of each SAE to each specific study treatment (if there is more than one study treatment), complete the SAE Report Form in English, and send the completed, signed form along with the Novartis provided fax cover sheet to the Novartis Oncology Drug Safety and Epidemiology (DS&E) department by fax ([contact]) within 24 hours..

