12.0 Statistical Considerations

12.1. Study Design/Endpoints

The required sample size for this trial is 43 patients, using a Simon two-stage design. The sample size justification and details are below.

We will conduct a single arm Phase II study to assess the efficacy of everolimus in patients with ≥ 3 cm sporadic AMLs. Response for a patient will be defined by a decrease in size of $\geq 25\%$ after 4 cycles of treatment.

We will implement an optimal two-stage Simon design for this trial. The new treatment would be of interest if the proportion, p , of responding patients is at least 25%. A proportion of patients with a response rate of less than 10% will be of no interest. Forty three (43) patients will allow us to test the null hypothesis: $p \leq 10\%$ against the alternative hypothesis: $p \geq 25\%$ at the 5% level of significance (α) with 80% power for a one-sided test. The early stopping point is 18 patients for both efficacy and toxicity. For efficacy, if 2 or fewer patients respond among the first 18 patients then the null hypothesis will not be rejected and the trial will be terminated. The probability of early stopping under the null is 73%. If the trial progresses until 43 patients are evaluated and 8 or more patients respond, then the null hypothesis will be rejected.

For toxicity, the trial will be paused and termination considered if out of the first 18 patients, 3 or more come off trial due to any adverse events as defined in the protocol. If the study proceeds to stage II (total enrollment = 43 patients), the trial will be paused and termination considered if at any point 8 or more patients come off trial due to any adverse events as defined in the protocol. If the true rate of any adverse events necessitating a patient to come off trial is 20%, the probability of early stopping is 73%; if the true rate of any adverse events necessitating a patient to come off trial is 5%, the probability of early stopping is 6%. Pause and

termination consideration for toxicity will occur, either early or finally, with probability 81% if true toxicity proportion is 20%; and 6% if it is 5%.

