To ensure oversight with respect to toxicity, an interim review will be conducted if the early stopping rule for toxicity is reached in the first 18 patients. For this interim review, all available data related to primary and secondary efficacy and toxicity endpoints will be collected, summarized and presented. The data will be reviewed at a meeting of the invested trial parties, including but not limited to investigators at all participating sites (PIs or representatives at outside centers may call in to the meeting), staff on the research team, members of the FCCC Investigator Sponsored Research Unit, and statistics team. A summary recommendation will emerge from the meeting as to whether the study should be terminated or modified to a new dosing schema. This recommendation will be forwarded to the FCCC DSMB for signoff. Study accrual will halt until the outcome of the interim review is accepted by the FCCC DSMB. If the DSMB does not concur with the findings of the Investigator Meeting, the local FCCC IRB will review the trial for final decision.

In secondary analyses we will use graphs, standard descriptive statistics (mean, median, minimum, maximum, standard deviation, two-sided 95% confidence intervals) and Generalized Estimating Equation methods to characterize and model longitudinal health-related quality of life (HRQoL) measurements. Tumor regrowth kinetics will be characterized by the percent change in volume from the date of everolimus treatment termination. Values will be summarized using plots and standard descriptive statistics (mean, median, minimum, maximum, standard deviation, two-sided 95% confidence intervals) separately for each measurement following treatment discontinuation. Safety and tolerability objective will be measured by the incidence of adverse events, serious adverse events, deaths and laboratory abnormalities. Spearman's correlation coefficients will be computed to estimate the association between the largest percentage volumetric response from baseline with levels of perfusion/angiogenic content/vascularity of baseline tumor as measured by DCE MRI.

We will tabulate the frequencies of all grade 2 or higher adverse events as defined by NCI CTCAE version 4 criteria. The criteria are available online at <http://ctep.cancer.gov/reporting/ctc.html>.

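### The toxicity rule in section 12.1 counts adverse-event removals without weighting, so a drug-related death need not pause accrual; a separate trigger would be a cheap improvement

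*Combined protocol and SAP*

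**What the plan says.** Section 12.1 sets two count limits. In stage 1 the trial is "paused and termination considered if out of the first 18 patients, 3 or more come off trial" owing to any adverse event. In stage 2 the limit is 8 or more, which the stated probabilities show to be cumulative over 43 patients.

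The formal consequence is described for stage 1 only: "an interim review will be conducted if the early stopping rule for toxicity is reached in the first 18 patients". Accrual then halts until the DSMB accepts the outcome. That review is to decide "whether the study should be terminated or modified to a new dosing schema", and for it "all available data related to primary and secondary efficacy and toxicity endpoints will be collected, summarized and presented".

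Death is covered elsewhere:

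- Section 9.1.2: "A serious adverse event is an AE that is fatal or life threatening". Section 9.1.3 has "Grade 5: Death related to AE" as the top severity grade.
- Section 10.2: sites must "report all SAEs that occur on or after the first day of study treatment to the sponsor within 24 hours" of learning of them. Section 10.3 sends them to the drug supplier within 24 hours as well.
- Sections 10.1 and 10.2: serious events go to the IRB, whether or not they were expected.
- Section 10.3: "SAEs that are related, unexpected, fatal, or life-threatening are reportable" to the FDA within 7 calendar days.
- Section 13.1: serious events are reviewed in real time by the site investigator, then by the research unit and the sponsor-investigator.
- Section 13.2: the DSMB may recommend ending accrual, but its role is advisory.

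**The concern.** The only automatic brake on enrolment is a count in which every removal has equal weight. Section 6.4.7 takes a patient off study for non-infectious pneumonitis of any grade, so a symptom-free radiological finding and a fatal event each add one. One or two drug-related deaths in the first 18 patients, or deaths in stage 2 with fewer than 8 removals in total, would not by rule pause anything.

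This matters because the protocol itself names fatal outcomes with everolimus (hepatitis B reactivation, renal failure and Pneumocystis pneumonia in 6.2, infection in 6.4.2, pneumonitis in 6.4.7), and section 3.0 stresses that the disease is not malignant. Tolerance for a treatment-related death should therefore be low. Under the current text, new patients may be enrolled while a death is being assessed unless someone chooses to stop.

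**Working it through.** **1. The plan's own figures.** Let X1 be the number of removals among the first 18 and X2 the number among the next 25, both binomial with removal rate p.

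Early pause: P(X1 ≥ 3 | 18, p).

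- p = 20%: 0.729 (stated 73%)
- p = 5%: 0.058 (stated 6%)

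Early or final pause: the early probability plus the sum over x = 0, 1, 2 of P(X1 = x) × P(X2 ≥ 8 − x | 25, p).

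- p = 20%: 0.729 + 0.086 = 0.814 after rounding (stated 81%)
- p = 5%: 0.0581 + 0.0003 = 0.058 (stated 6%)

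All four reproduce, and the overall figures confirm that the limit of 8 is cumulative.

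**2. Inputs for the death question.** The rate of other adverse-event removals, q, is taken as 5% and 20% (the two rates in 12.1) and 8% (the EXIST-2 discontinuation figure in section 1.5). A death is assumed to count as coming off trial, the reading most favourable to the rule. Removals are independent between patients.

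**3. One death in the first 18.** The count stays below 3 if at most one of the other 17 is removed: P(X ≤ 1 | 17, q) = (1 − q)^17 + 17q(1 − q)^16.

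- q = 5%: 0.418 + 0.374 = 0.792
- q = 8%: 0.242 + 0.358 = 0.600 after rounding
- q = 20%: 0.023 + 0.096 = 0.118 after rounding

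**4. One death in stage 2, stage 1 having passed.** With i removals in stage 1 (i = 0, 1 or 2), the cumulative total stays at 7 or fewer if the other 24 stage 2 patients give at most 6 − i removals. The probability is the sum over i of P(X1 = i | X1 ≤ 2) × P(X ≤ 6 − i | 24, q).

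- q = 5%: 0.998
- q = 8%: 0.983
- q = 20%: 0.066 × 0.811 + 0.299 × 0.656 + 0.635 × 0.460 = 0.542

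**5. Unconditional size, illustration only.** The documents give no drug-related death rate, so d is assumed to be 0.1% to 0.5% per patient. The chance of at least one such death with no count pause in the first 18 is the sum over k = 1, 2 of P(k deaths | 18, d) × P(X ≤ 2 − k | 18 − k, q).

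| q | First 18 | All 43, if enrolled |
|---|---|---|
| 5% | 1.4% to 6.7% | 3.7% to 16.8% |
| 8% | 1.1% to 5.1% | 3.0% to 13.8% |
| 20% | 0.2% to 1.0% | 0.5% to 2.2% |

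The last column is upper-end. With the efficacy stop included, the q = 5% entry becomes about 2.0% to 9.4% at a 10% response rate and 3.4% to 15.5% at 25%. It also counts deaths after accrual closes, when a pause would do nothing. At 2 patients per month, 16 to 24 weeks of treatment (about 3.7 to 5.5 months) leaves roughly 7 to 11 patients on drug at that point.

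**The case against.** The strongest reply is that 12.1 monitors a removal rate and does that correctly. A single-death trigger is a different safeguard, and leaving a rare event to real-time review and the DSMB is a legitimate choice. That stands, and it is why this is an improvement and not a correction.

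A reader might infer that a death would go unnoticed, or that enrolment would continue regardless. The documents do not support that. Reporting to the sponsor, the drug supplier and the IRB is mandatory, and the IRB duty in 10.1 and 10.2 does not depend on expectedness, so even a death from a harm already named in the protocol reaches it. Any of these bodies may well prompt a pause. None is required to.

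A reader might also take the unconditional percentages as the expected frequency of the problem. They rest on an assumed death rate. The EXIST-2 summary in section 1.5 lists grade 3 and 4 events and mentions no grade 5, though it does not say there were none. Eligibility excludes HIV, hepatitis B and C, active infection and uncontrolled lung disease, and treatment is limited to 6 cycles. The true rate may be low.

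Section 13.2 defers the DSMB's duties to a separate Data and Safety Monitoring Plan that could not be checked and may already contain a trigger. Section 6.4.1, read literally, ends the trial on hepatitis B reactivation. In context it more likely means that patient's participation, and in either case it covers one cause only.

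**Conclusion.** The point holds as a low-cost safety improvement. No available text requires accrual to pause after a drug-related death. The best measure of the gap is conditional, because it needs no death rate: after one death the count rule produces no pause with probability 79% (first 18) or 99.8% (stage 2) at 5% other removals, 60% or 98% at 8%, and 12% or 54% at 20%. So the rule is least likely to respond to a death when the drug otherwise looks tolerable, and it responds less in stage 2 than in stage 1.

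These figures assume that deaths count as removals and that removals are independent. The conclusion about the protocol text is firm; whether the trial as a whole lacks the safeguard depends on the monitoring plan.

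**What to change.** Add to 12.1:

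> Independently of the counts above, any grade 5 adverse event at least possibly related to everolimus, in either stage, pauses accrual until a safety review by the 12.1 review group has been held and the FCCC DSMB has accepted its recommendation to continue unchanged, modify or terminate. The review also decides whether patients on treatment continue everolimus. It uses safety data and needs no efficacy summary. If the DSMB does not concur, the FCCC IRB decides, as for the existing interim review.

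Separate wording is needed because the existing review does not list continuing unchanged as an outcome and calls for efficacy data. If the Data and Safety Monitoring Plan already has such a trigger, a cross-reference in 12.1 is enough.

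The provision uses the existing severity grades, attribution scale, review group and DSMB, and leaves the count limits and their stated probabilities unchanged. The cost is a short pause after a death that may prove unrelated. At 2 patients per month, an assumed pause of 2 to 8 weeks (about 0.5 to 1.8 months) costs about 1 to 4 patients of accrual time. At the assumed death rates the trigger would fire in at most 1 − (1 − d)^43 = 4.2% to 19.4% of trials that enrol all 43.

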3.0 Study Plan

After confirming eligibility criteria, patients will be enrolled in this study. Volumetric and perfusion/vascularity analyses will be done by DCE-MRI at baseline. Patients will then receive everolimus 10 mg daily. Treatment duration will be continuous for 4 cycles unless treatment is discontinued.

After 4 cycles of treatment, repeat imaging with DCE-MRI will be performed to assess tumor size kinetics (sum of volumes of all target AMLs identified at baseline). If the tumor has decreased in size by greater than or equal to 25% and no new AMLs greater than 1 cm in longest diameter have appeared, then the drug will be continued for another two cycles (6 cycles total treatment). If on the other hand the tumor has grown or decreased by less than 25% or there are new AMLs (at least 1 cm in longest diameter), then the drug will be discontinued.

At the end of cycle 6 and 12 months after start of therapy with everolimus, imaging via DCE MRI will be repeated to assess growth/regrowth kinetics/qualitative perfusion.

If for any reason a patient terminates treatment with everolimus earlier than the end of cycle 4, all imaging will still be performed and used for the statistical analysis and primary endpoint calculations. Given that therapy with everolimus has potential toxicity and that the disease in question (sporadic AML) is not a malignant condition, patients will not be replaced if they drop out, in a way signaling that the therapy may not be feasible. If a patient receives at least one dose of everolimus they will be included in the analysis. If a patient does not get imaged after 4 cycles of treatment, for the purposes of statistical considerations they will be considered a non-responder.

Treatment related toxicities and QOL will be assessed at baseline, day 1 of each 28 day cycle, at drug discontinuation and at the last study visit

Tissue for exploratory objectives will be collected at baseline only if available from archival tissue. Additional tissue will also be collected if the patient undergoes a partial or complete nephrectomy or embolization during the study period for the AML. Serum at baseline will also be collected for cfDNA and other future potential correlative studies.

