5.4. **Criteria for Discontinuation**

Patients will be removed from treatment if one of the following criteria applies:

- Disease progression including:
 - Bleeding or pain
 - Requirement for surgical or percutaneous intervention
 - Greater than a 25% increase in tumor volume of AML
- Intercurrent illness that prevents further administration of treatment

- Unacceptable adverse events
- Treatment is temporarily held for > 21 days
- Patient becomes pregnant
- Patient decides to withdraw from the study
- General or specific changes in the patient's condition that render the patient unacceptable for further treatment in the judgment of the investigator.

The reason for discontinuation and the date the patient was removed must be documented in the medical record and case report form.

5.5. **Optional Tissue and Blood Collection for Exploratory Objectives**

At time of trial initiation, patients will be consented to allow the use of their tissue and blood for future research, specifically including, but not limited to, the analysis of mTOR alterations, VEGF pathways and tumor genome sequencing (e.g. mutations (AKT/PI3K, PTEN), amplifications, deletions in TSC1 and TSC2).

At screening, if archival biopsy tissue of the AML is available, unstained slides will be requested. If a patient undergoes a clinical procedure where tissue will be obtained during the study, that tissue will also be collected for exploratory objectives. Biopsy, resection, and/or percutaneous intervention will be performed entirely at the discretion of the treating clinician based on individual clinical scenarios and needs.

An EDTA and red top tube will be collected to provide plasma, serum and peripheral blood mononuclear cells (PBMCs). All biological samples will be stored at Fox Chase Cancer Center for possible future research.

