8.0 Study Calendar

	Screening ^A	Day 1 of Cycles 1, 3, and 5 ^H	Day 1 of Cycles 2, 4, and 6 ^H	Cycle 5 Day 1 ^H	Cycle 6 Day 28 ^H	Off Treatment	12 Month Follow-up ^H
Informed Consent	X						
Medical History	X						
Concurrent Medications	X	X	X			X	
Height	X						
Weight	X	X	X			X	
Physical exam	X	X	X			X	
Vital signs ^B	X	X	X			X	
ECOG Performance Status	X	X	X			X	
Serum chemistry ^C	X	X	X			X	
FKSI QOL Assesment	X	X	X			X	X
CBC w/diff, plts	X	X	X			X	
Fasting serum cholesterol & Triglycerides & Hgb A1c	X	X				X	
EKG	X						
Hepatitis B, Hepatitis C & HIV Screening ^D	X						
Tumor Measurements	X			X	X		X
Optional Correlative Tissue Collection		X ^E	X ^F				
Optional Correlative Serum Collection		X ^E		X	X		X
Serum Pregnancy Test ^G	X						
Urine or Serum Pregnancy Test ^G		X	X			X	
Adverse Event Assessment		X	X				

- A: Screening H&P, EKG and all labs must be ≤ 14 days prior to registration. Tumor measurements and radiologic evaluations must be ≤ 30 days prior to registration. Pre-study assessments may be used for cycle 1 day 1
- B: Screening blood pressure must be assessed with three measurements at approximately 2-minute intervals.
- C: Serum chemistry includes Albumin, alkaline phosphatase, total bilirubin, bicarbonate, BUN, calcium, chloride, creatinine, fasting glucose, LDH, phosphorus, potassium, total protein, SGOT [AST], SGPT [ALT], sodium, glucose.
- D: Screening for Hepatitis B will include, HBsAg, HBsAb, and HBc Ab. A positive HBsAb result in patients who have received prior HBV vaccination will not lead to exclusion from the study as long as HBsAg is negative. Screening for Hepatitis C will be via Hepatitis C antibody. If positive confirmation with quantitative RNA PCR will be done.
- E: If archival tissue is available from a previous renal lesion biopsy, unstained slides will be collected as detailed in 5.5. Correlative blood and tissue for this timepoint will be collected at Cycle 1 Day 1 only.
- F: If a percutaneous intervention or surgical intervention is performed during the study, tissue will be collected for further a analysis as detailed in 5.5
- G: Women of Childbearing Potential Only. Serum pregnancy test at time of screening must be completed **<72 hours** before registration
- H: All study visits have a window of +/- 5 days. Ensure that patients are given enough study drug to last until their next visit if scheduled more than 28 days from start of a cycle.

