11.0 Measures of Effect

11.1. Response Evaluation Utilizing DCE-MRI

DCE-MRI assessments will be performed at baseline, on Cycle 5 Day 1, on Cycle 6 Day 28, and 12 months after the start of treatment. The Cycle 6 Day 28 MRI and the 12 month MRI will be done even if patient doesn't continue onto cycles 5 and 6.

Location and size of the IV, as well as type and amount of contrast and injection rate should be the same for all time points of each individual patient. These can be different between patients.

Protocol should contain at minimum breathhold axial T1W in and out of phase multiplanar gradient echo sequence. To evaluate volume of the index lesion perform axial and coronal breathhold T1W 3-d gradient echo sequences with and without fat saturation (VIBE, LAVA/FAME and THRIVE for Siemens, GE and Philips respectively). Then, dynamic pre and post contrast enhanced nonbreathhold coronal T1W fast 3-d gradient echo sequences to run for two minutes. Each individual volume acquisition time should be maximum 4-5 seconds. These should be lower resolution with 5 mm slice thickness and adjust slice number to cover the size of the index lesion usually 15-20 slices. Phase encoding of 128 or less to keep acquisition time of less than 5 seconds. Patients should be instructed to perform shallow breathing. Start injection of the contrast 15 seconds after the start of the acquisitions. Acquisitions stop at 2 minutes after the start and at 2.5 minutes repeat the coronal and axial breathhold T1W fast 3-d gradient echo sequences with fat sat in that order.

Choose a central slice of the index lesion on the pre and post coronal breathhold images and trace the perimeter and get a signal intensity number for both. If possible choose a slice with a large soft tissue component and trace that separately pre and post. Calculate a percent enhancement as follows: $(\text{Post} - \text{Pre}/\text{Pre}) \times 100$. Dynamic data can be used to choose post time point with maximum enhancement. If possible, calculate an AUC 45 (area under the curve for 45 seconds) from the dynamic data. Volumes can be calculated on the breathhold 3-d sequences with or without fat sat. If dynamic sequences are unusable secondary to artifacts, then percent enhancement can be calculated from the breathhold 3-d T1W sequences with or without fat sat.

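### Regrowth is summarised as raw percent change with no scaling for time off drug, so month 12 pools about 197 and 253 days in a way tied to response, and patients who stop between scans have no scheduled termination volume

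*Combined protocol and SAP*

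**What the plan says.** Section 2.2 makes growth kinetics after everolimus a secondary objective, and section 1.5 names quantifying regrowth after discontinuation as one of three aims. Section 12.1 gives the analysis: "Tumor regrowth kinetics will be characterized by the percent change in volume from the date of everolimus treatment termination". Plots and descriptive statistics are then given "separately for each measurement following treatment discontinuation". No section divides by time off drug or models volume against time. Generalized estimating equations are named only for quality of life.

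The scans run on a different clock, counted from the first day on drug. Section 11.1: "DCE-MRI assessments will be performed at baseline, on Cycle 5 Day 1, on Cycle 6 Day 28, and 12 months after the start". That section adds: "The Cycle 6 Day 28 MRI and the 12 month MRI will be done even if patient" does not go on to cycles 5 and 6. Section 3.0 ends treatment after cycle 4 (4 × 28 days) for patients with less than a 25% reduction or a new AML of at least 1 cm, and after cycle 6 for the rest.

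Section 3.0 also covers early stopping: "If for any reason a patient terminates treatment with everolimus earlier than the end of cycle 4, all imaging will still be performed". It adds no scan at the time of stopping. In the section 8.0 study calendar, the tumor measurements row has no mark in the Off Treatment column. Section 5.4 lists reasons for stopping that can arise on any day, among them "Requirement for surgical or percutaneous intervention". Section 12.1 has no rule for volumes measured after such an intervention.

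**The concern.** A percent change describes kinetics only alongside the time over which it accrued. Here that time differs between patients by design, and it differs along the line a reader is most likely to look at: patients who reached the 25% reduction stay on drug longer and so have a shorter off-drug interval at month 12. Raw month-12 changes for responders and non-responders would differ even if every tumour regrew at the same speed.

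There are two further gaps. For a patient who stops between scans, the starting volume that 12.1 calls for is not scheduled to be measured. And a target AML that has been embolised or resected would count as shrinking off drug. Both would have to be settled after the data are seen.

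**Working it through.** **Plan's own figures.** The documents state no off-drug interval and no regrowth rate, so there is nothing to reproduce for this analysis. The primary design figures in 12.1 do reproduce (early stopping under the null 0.734, one-sided alpha 0.0480, power 0.8003) and do not depend on regrowth.

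**Inputs.** 28-day cycles (section 5.0); stop after 4 or 6 cycles (3.0); scans at Cycle 5 Day 1, Cycle 6 Day 28 and 12 months from start (11.1), taken as days 112, 168 and 365.

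**Days off drug = scan day − stop day.**

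| Stop | At Cycle 6 Day 28 | At month 12 |
|---|---|---|
| Day 56 (example) | 168 − 56 = 112 | 365 − 56 = 309 |
| Day 112 (4 × 28) | 168 − 112 = 56 | 365 − 112 = 253 |
| Day 140 (example) | 168 − 140 = 28 | 365 − 140 = 225 |
| Day 168 (6 × 28) | 0 | 365 − 168 = 197 |

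The ratio for the two main groups at month 12 is 253/197 = 1.28. The calendar states: "All study visits have a window of +/- 5 days". Applied at both ends, this gives 187–207 and 243–263 days, which do not overlap. The difference is therefore built in and is not visit noise.

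**Effect on the raw figure.** Assumption: every tumour regrows at one constant rate g per month. Percent change = 100 × (exp(g × days/30.44) − 1). The pooled mean is s × (197-day value) + (1 − s) × (253-day value), where s is the share completing six cycles and all others stop at day 112. The shares 10% and 25% are the response rates that anchor the design in 12.1.

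| Assumed rate | Day-112 stoppers | Six-cycle completers | Pooled, s = 10% | Pooled, s = 25% |
|---|---|---|---|---|
| 5% per year, g = ln(1.05)/12 | 3.4% | 2.7% | 3.4% | 3.2% |
| g = 0.01 | 8.7% | 6.7% | 8.5% | 8.2% |
| g = 0.02 | 18.1% | 13.8% | 17.7% | 17.0% |
| g = 0.04 | 39.4% | 29.5% | 38.5% | 37.0% |

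The contrast between stopping groups is visible; the pooled mean hardly moves.

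**Between-scan stoppers.** Take a day-56 stopper at g = 0.02. True regrowth by month 12 is 100 × (exp(0.02 × 309/30.44) − 1) = 22.5%. If the Cycle 5 Day 1 scan stood in as the termination volume, the figure would cover only 253 days and read 18.1%. A rate between the two post-stop scans, ln(V365/V112) ÷ (253/30.44), still returns 0.02 under the constant-rate assumption.

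**Volumes available at or after stopping, if all scans are done.** Stop before Cycle 5 Day 1: three. Stop at Cycle 5 Day 1: three. Stop during cycles 5–6: two. Stop after cycle 6: two.

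**The case against.** The case for leaving 12.1 alone is reasonable. The analysis is secondary and descriptive, with no comparator and no decision resting on it. Plots are planned, and anyone with the dates can compute rates later. Read by scheduled scan, 12.1 already separates Cycle 6 Day 28 from month 12, which leaves a 1.28-fold spread and a small pooled effect. A log-volume rate also assumes a constant rate. If regrowth is fastest just after stopping, scaling will not make the groups comparable. All of this stands, and it limits the weight of the point. It does not remove the gaps: 12.1 does not say that the plots use time off drug, plots do not repair the summary statistics, and no reference volume is defined for between-scan stoppers.

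A reader might infer more than the documents support:

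- *The first post-stop measurement mixes 56 and 197 days (197/56 = 3.5-fold).* This follows only if the summaries go by scan order. 12.1 does not say so, and the scheduled scan is the more natural reading.
- *Regrowth could change sign if baseline were the reference.* 12.1 measures from the termination date, so a baseline reference would contradict its text.
- *Up to 7 of 43 patients are affected, because the stage II toxicity pause comes at 8.* 12.1 also pauses at 3 of the first 18. Adverse-event stops need not fall between scans, and other reasons for stopping exist. The number is unknown.
- *No between-scan stopper has a volume at stopping.* The 5.4 criterion of more than a 25% volume increase implies a measurement in some cases, although none is scheduled outside the listed scans.

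Separately, sections 6.3.2, 6.4.4 and 6.4.7 take some patients off study, while 3.0 and 5.3 keep imaging or follow-up. These passages must be reconciled, because they determine who has regrowth data.

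**Conclusion.** The point holds as a minor, cheap improvement. The intervals of 197 and 253 days, and their link to response, follow from the protocol's own schedule. So does the missing termination scan. The percentage differences (18.1% against 13.8% at 2% per month) rest on an assumed common constant rate, because the documents give none. They show that a responder against non-responder reading of raw month-12 change would mislead. They do not show that the pooled mean is materially wrong. A reader might also infer a threat to the trial's main conclusion; there is none, since the primary test uses response after four cycles and does not involve regrowth.

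**What to change.** In section 12.1:

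- Report regrowth as change in ln(volume), or percent change, per month off drug, using actual last-dose and MRI dates.
- Present it by stopping group (at Cycle 5 Day 1, after cycle 6, between scans), with percent change by scheduled scan and days off drug alongside.
- For between-scan stoppers, calculate the rate only between scans taken after stopping. Do not use baseline or a later scan as the termination volume. State how many have no computable rate.
- Report volumes measured after intervention on a target AML separately, and give the summary with and without them.
- Plot each patient's volume against months off drug, marking interventions.

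The cost is analysis wording, with no added scans. Section 5.4 already requires the removal date to be recorded, section 5.0 provides a pill diary for the last dose, and intervention by one year is already an outcome in 2.2.

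There are downsides. A constant rate cannot be checked in patients with only two volumes at or after stopping. Rates for between-scan stoppers begin some time after the drug ended. Scaling does not remove the link between interval and response, and the stopping groups will be small: at 10% to 25% of 43, about 4 to 11 six-cycle completers.
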